4.4 Sample size calculation

RCT

The primary objective of the study is to realize an efficient allocation of resources to the available treatment options in advanced PD. For this, primarily an economic evaluation will be carried out and the sample size has been calculated accordingly. Society's willingness-to-pay (WTP) per Quality Adjusted Life Year (QALY) may be indicative of whether or not CLI is affordable compared to DBS. The Dutch Raad voor de Volksgezondheid (RvZ) reported a value of €80,000 per additional QALY in 2006 as a potential upper limit of affordability. Explicitly, the figure is reported by the RvZ as a potential, but also unofficial limit: it should

Version 7: 23-10-2019 16 of 48

not be taken as a definite one. Other arguments based on patient preference or access to health care should be taken into account as well. Considering that CLI may be a less invasive intervention and access to health care is easier to facilitate when two interventions can be provided, a more lenient upper limit for the extra societal costs per additional QALY may be appropriate here. We propose a sample size calculation based on a WTP per additional QALY of €120,000 (50% above the RvZ figure). Based on the net health benefit formula suggesting that differences in QALYs between the interventions should be larger than the difference in costs (i.e., €34,174 a year) divided by the maximum WTP (i.e., €120,000 per QALY) in order for one intervention to be accepted as more efficient than another intervention, CLI treatment should at least outperform DBS treatment by 0.2847 QALY per year. Based on literature data with comparable costs estimates, [6] we anticipate standard deviations (SD) for QALYs up to 0.35 and for total costs up to €10,000 (factoring in a 12-month follow-up and non-responders).

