To achieve 80% power and given a two-sided significance level of 0.05, up to 26 patients per group (or 52 in total) are needed to detect a difference of at least 0.2847 QALY for WTP-values up to €120,000 and a worst case scenario of zero correlation between costs and clinical effect, using a two-group t-test. Accounting for a possible dropout of 20%, we will randomize 66 patients (33 per group). With this sample size and given the same test conditions (power, type-I error rate, test chosen, drop-out rate) we are also able to detect a difference in mean PDQ-39 scores between both groups of 11.9, assuming an expected mean score of 32 in the DBS group and a standard deviation of 15.

Motivation for standard deviations for QALY

Literature data [8-10] show that the standard deviation for PDQ-39 scores from operated PD patients equals 15 points and that a 4 to 5 points difference is associated with a QALY difference of approximately 0.1,[16] suggesting a standard deviation for QALYs of up to 0.35.

Patient preference trial

We (conservatively) estimate that during the inclusion period a total of 180 patients (60% of the eligible patients) may decline to participate in the RCT, but are willing to take part in the preference observational study. Based on our clinical experience it is expected that 60% of these patients (n=108) prefers DBS, against 40% (n=72) preferring CLI.

When comparing the effect of DBS treatment of patients who express a preference for that treatment with the effect of DBS treatment in the randomised patients, and given the same test conditions (power, type-I error rate, two group t-test) we are able to detect a difference in

Version 7: 23-10-2019 17 of 48

mean PDQ-39 scores between both groups of 8,4, assuming an expected mean score of 32 in the randomized DBS group and a standard deviation of 15.

In case only 120 patients (40% of the eligible patients) agree to take part in the preference observational study, we are able to detect a difference in mean PDQ-39 scores between both DBS groups of 8,9.

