8.8 Secondary study parameter(s)

RCT

The main clinical analysis of the study consists of a comparison between the trial treatment groups (DBS versus CLI) of the primary clinical outcome (PDQ-39) 12 months after the start of the study treatment. First, the follow-up difference between PDQ-39 scores will be analysed using a two-group t-test. Second, the PDQ-39 follow-up scores will be further investigated using multiple linear regression taking into account patients' PDQ-39 baseline values, the stratifying variables (experience of the including centre with DBS and CLI; response to Levodopa) and (if necessary) for clinically relevant baseline imbalances. Additionally, the repeated data structure will be investigated with a linear mixed model. The same analyses will be performed for the 24 and 36 month outcomes. With regard to the comparisons of the other secondary outcomes PD motor symptoms (MDS-UPDRS, CDRS, 3-day motor symptom diary), non-motor symptoms such as autonomic functions and sleep (Non Motor Symptom Checklist, Rotterdam Symptom Checklist), PD-medication, neuropsychological and psychiatric assessment, disability, functional health status (ALDS), patient and physician preferences, patient satisfaction, adverse effects and complications, treatment failure, stopping treatment, starting with the alternative than initially started treatment, caregiver burden and medical and non-medical care costs (iMCQ, iPCQ) we will use the appropriate parametric and non-parametric statistics. In all analyses, statistical uncertainties will be expressed in 95% confidence intervals.

Patient preference trial

As mentioned before a patient preference observational study will be conducted to asses external validity of the randomized controlled trial results. The primary clinical outcome of the non-randomized group and randomized group will be compared using the two-group t-test and linear regression, whereas baseline characteristics will be compared with the

Version 7: 23-10-2019 32 of 48

two-group t-test and Chi-square test, when appropriate. Finally, the impact of the treatment on the PDQ-39 follow-up scores of the randomized and non-randomized group will be analysed using multiple linear regression, adjusting for relevant imbalanced baseline variables and randomized status (agreeing to randomization or not).

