After it proved challenging to include patients in other centers than the primary including hospital (Amsterdam UMC), the recruitment and consent procedure was adjusted twice to enhance inclusion in the ancillary patient preference observational arms in other participating centers. First, it was no longer obligatory to sign the informed consent form face-to-face with the researcher for eligible patients who did not consider participation in the RCT but were willing to be included in the ancillary patient preference observational arms (2016). Patients could return the informed consent form by mail as of then. Second, treating physicians from non-participating centers were also allowed to register patients for the ancillary patient preference observational arms, after which the research team contacted the patient and enrolled them if eligible (2019). Furthermore, to enhance recruitment in the RCT in other centers, treating physicians were contacted frequently and patients were informed through the Dutch Parkinson Society. This did not lead to protocol changes.

Concerning the primary outcome, the usage of the Parkinson's Disease Questionnaire-39 (PDQ-39) was operationalized as follows: the difference between the two treatment groups (*i.e.*, DBS and CLI) in change from baseline to 12 months on the PDQ-39 summary index score. The change (*i.e.*, from baseline to 12 months) on total PDQ-39 was chosen as this score displays alteration in disease related quality of life after instalment of the allocated treatment and therefore is largely independent of possible differences in baseline values in the relatively small populations. The PDQ-39 has been a frequently used outcome measure in clinical trials for PD.⁴⁻⁶ Use of repeated PDQ-39 measures was planned in the original design; a PDQ-39 assessment was planned at the nine months follow-up time-point to be able to pool data with a designed similar trial by another study group. Unfortunately, that study and planned international pooling of data never came into existence. Because there was a limited number of repeated PDQ-39 measurements (*i.e.*, at baseline, nine months, and 12 months follow-up), no major differences between both follow-up points were

expected. Also, up to 2016 the nine months visits proved incomplete with regard to the PDQ-39 assessments. Therefore, it was decided not to perform a repeated measurement assessment.

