For normally distributed data means and standard deviation were presented, for non-normally distributed data medians and interquartile ranges. For the Hoehn & Yahr stage median and range were reported.

Analyses

Randomized controlled trial

Reported outcomes were presented in Table SAP2 (part A and B). The main publication consisted of analyses in the mITT population. The analyses in ITT, as-treated and per-protocol populations were presented in supplements.

Analysis of main clinical outcome

The main analysis regarding the clinical outcome was the between-group difference in change from baseline to 12 months follow-up in total PDQ-39 summary index score in the mITT population, using a two-group *t*-test. Additionally, a multiple linear regression analysis was performed taking into account the stratifying variable (level of experience of the treatment center) and (if necessary) clinically relevant baseline imbalances. To assess whether the baseline value of the PDQ-39 served as an effect modifier (meaning that the association between intervention and outcome differed according to baseline PDQ-39) an interaction term was used in the regression analysis. In case of a significant interaction term, the analysis was additionally performed in two separate strata: one with patients with a median PDQ-39 or below and the other with patients with a PDQ-39 above median.

Sensitivity analyses

Sensitivity analyses concerning missing data as described in the paragraph “Patient replacement and missing data” were performed in the mITT population. To further assess robustness of the mITT analysis for the main clinical outcome additional sensitivity analyses were performed.

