The primary health outcome in the cost-effectiveness analysis was the change in the PDQ-39 between baseline and 12 months after randomization. The change score showed the increase or decrease in number of difficulties across eight different dimensions of health (including mobility, activities of daily living, emotional well-being, and stigma) as experienced by patients in the preceding month. Dimension scores are coded on a scale of 0 (perfect health as assessed by the measure) to 100 (worst health as assessed by the measure). The change score was defined as the mean score on the eight scales at month 12 minus the mean score at baseline, in theory ranging from -100 to +100 with a score of 0 representing 'no change'.

The primary health outcome in the cost-utility analysis was the number of QALYs. Patient's health status was assessed with the EQ-5D-3L at baseline, one week, three months, six months, nine months, and 12 months post randomization. The EQ-5D contained five items: mobility, self-care, usual activities, pain/complaints, and mood (anxiety/depression).³¹ Each item had three response options: no problems, some problems, or serious problems. EQ-5D scoring profiles at successive measurements were converted into health utility scores using general population based tariffs of time trade-off ratings of health states.³² QALYs were calculated by taking the product sum of the health utility scores during follow-up and the interval lengths in years in-between successive measurements.

Health economic analysis methods

Analysis population

The CEA and CUA were done with the modified intention-to-treat population (see page 9) with references to the CONSORT-flow diagram in Figure SAP-1 and the baseline characteristics of the two RCT-subpopulations in Table EE1. Summary statistics for health utility scores at baseline were included in the manuscript text.

Cost-effectiveness threshold

The applied cost-effectiveness threshold for the sample size calculation was €120,000 as described and substantiated in the published study protocol.¹

Statistical decision rules

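### The main PDQ-39 test and the base-case QALY comparison fix the baseline coefficient (at 1 and at 0); estimating it by regression would usually be more precise, at no data cost

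*SAP*

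**What the plan says.** **PDQ-39.** Under Analysis of main clinical outcome, the SAP tests "the between-group difference in change from baseline to 12 months follow-up in total PDQ-39 summary index score in the mITT population" with a two-group t-test. Its Synopsis of study protocol development argues that the change score shows what happened after treatment and "therefore is largely independent of possible differences in baseline values in the relatively small populations".

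An additional regression takes in centre experience and, conditionally, "if necessary) clinically relevant baseline imbalances. To assess whether the baseline value of the PDQ-39 served as an effect modifier". No rule says when an imbalance makes adjustment necessary, and baseline PDQ-39 is named only for the interaction check. Protocol section 8.8 was firmer: its second-step regression of follow-up scores included, without condition, "PDQ-39 baseline values, the stratifying variables (experience of the including centre with DBS and CLI; response to Levodopa".

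**QALYs.** The HEAP (Statistical decision rules) compares mean QALYs by bootstrapped two-sample t-tests with no baseline term. Baseline utility is available, since "health status was assessed with the EQ-5D-3L at baseline, one week, three months" and at later visits. It is used in two other places: "Summary statistics for health utility scores at baseline were included in the manuscript text" (Analysis population), and one scenario analysis subtracts each patient's baseline utility from the QALYs.

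**Planning figures.** Protocol section 4.4 says the trial can "detect a difference in mean PDQ-39 scores between both groups of 11.9, assuming an expected mean score of 32 in the DBS group" and an SD of 15. For QALYs it says "we anticipate standard deviations (SD) for QALYs up to 0.35".

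**The concern.** A t-test on change uses the baseline with its coefficient set to 1. A comparison of QALYs without baseline utility sets it to 0. The best value usually lies between, and regression estimates it from data already in hand.

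The SAP's reason for using change is not correct in general. With equal SDs at baseline and 12 months and correlation r, a baseline difference D between arms moves the change estimate by −(1−r)D. Change is free of baseline imbalance only as r approaches 1.

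What is at stake is precision. The PDQ-39 change is both the main clinical outcome and the effect in the ICER. The QALY difference drives the ICUR, the net health benefit and the acceptability curve.

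**Working it through.** **Inputs from Protocol section 4.4:** 26 evaluable patients per arm, two-sided α 0.05, power 80%, PDQ-39 SD 15, QALY SD up to 0.35, cost SD up to €10,000, willingness to pay €120,000. **Assumed:** r, because neither document gives it; equal SDs at baseline and 12 months; a lower QALY SD of 0.25 for comparison.

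**Reproducing the plan.** The standard error of a difference is SD·√(2/26). For SD 15 it is 4.16, and the noncentral t with 50 df gives a detectable difference of 11.89, the protocol's 11.9. The net-health-benefit SD is √(0.35² + (10,000/120,000)²) = 0.3598. For a difference of 0.2847 this gives 26 per arm by the normal approximation (power 79.9% by exact t), and 26/0.8 rounds up to 33 per arm.

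**PDQ-39.**
- SD of change: 15·√(2(1−r)).
- Residual SD after regression on baseline: 15·√(1−r²), with 49 df.
- Variance ratio, regression to change: (1−r²)/(2(1−r)) = (1+r)/2.
- Cost of estimating the slope: variance factor 1 + 1/(52−4) = 1.0208, included in the adjusted rows below.

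| Assumed r | 0.3 | 0.5 | 0.7 | 0.9 |
|---|---|---|---|---|
| SD of change | 17.75 | 15.00 | 11.62 | 6.71 |
| SE of change estimate | 4.92 | 4.16 | 3.22 | 1.86 |
| Detectable difference, change | 14.06 | 11.89 | 9.21 | 5.32 |
| Detectable difference, adjusted | 11.46 | 10.40 | 8.58 | 5.24 |
| Net variance saving | 34% | 23% | 13% | 3% |
| Shift in change estimate from a one-SE imbalance (4.16 points) | 2.91 | 2.08 | 1.25 | 0.42 |

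The shift is part of the SE in the second row, so it is not an extra bias. Power for 11.9 points, change versus adjusted, is 66% v 83% at r = 0.3, 80% v 89% at 0.5 and 95% v 97% at 0.7. Break-even is r = 2/1.0208 − 1 = 0.96. In 20,000 simulated trials per r, the SD of the estimate was 4.93 / 4.17 / 3.20 / 1.85 for change and 4.01 / 3.64 / 2.98 / 1.82 adjusted.

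The 11.9 was derived for a score with SD 15. The SD of change equals 15 only at r = 0.5, so the figure carries over to the SAP's analysis only there.

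**QALYs.** The residual SD is SD·√(1−r²), with the same factor 1.0208.

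| Assumed r with baseline utility | 0.3 | 0.5 | 0.7 |
|---|---|---|---|
| Detectable, unadjusted, SD 0.35 | 0.277 | 0.277 | 0.277 |
| Detectable, adjusted, SD 0.35 | 0.267 | 0.243 | 0.200 |
| Detectable, unadjusted, SD 0.25 | 0.198 | 0.198 | 0.198 |
| Detectable, adjusted, SD 0.25 | 0.191 | 0.173 | 0.143 |
| Net variance saving, QALY | 7% | 23% | 48% |
| Net variance saving, net health benefit at €120,000 (SD 0.35) | 7% | 22% | 45% |
| Power for 0.2847 net health benefit (79.9% unadjusted) | 82.5% | 88.7% | 96.6% |

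A one-SE imbalance in baseline utility shifts the unadjusted difference by r·SD·√(2/26), which is 0.029 / 0.049 / 0.068 at SD 0.35, inside its SE of 0.097. Break-even is r = √(1 − 1/1.0208) = 0.14. At r = 0 the adjusted detectable difference is 0.280 against 0.277.

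**The subtraction scenario.** With equal SDs its variance is 2(1−r) times the unadjusted variance, or 1.4 times at r = 0.3, so it loses precision whenever r is below 0.5.

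**The case against.** The case for leaving the plan alone is reasonable, and several parts of it stand.

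- **The planned tests are valid.** True. Apart from the separate effect of the mITT exclusions, which adjustment would not cure, there is no bias to remove.
- **Baseline PDQ-39 is already in a planned model.** A conventional interaction model does include its main effect. But unless baseline is centred, which the SAP does not mention, the arm coefficient is the effect at PDQ-39 = 0. In a simulation with r = 0.5 and an assumed baseline mean of 40, its SE was 11.0, against 3.6 for simple adjustment. It does not supply an adjusted main estimate.
- **The two QALY results bracket the adjusted one.** Often so. With QALY SD 0.35 and baseline-utility SD assumed at 0.25 to 0.35, they enclosed it in 98%, 96–100% and 56–100% of simulated trials at r = 0.3, 0.5 and 0.7. Bracketing shows sensitivity but adds no precision; the gap at a one-SE imbalance is 0.069 to 0.097 QALY.
- **Cost variance dilutes the gain.** This stands at low willingness to pay. At €20,000 per QALY the net-health-benefit saving is 2% / 8% / 16% at r = 0.3 / 0.5 / 0.7. At €500 per PDQ-39 point it is 15% / 8% / 3%. At the €120,000 used for sizing, little is lost.
- **The size is unknown.** Also true: the PDQ-39 saving runs from 34% down to 3% over the assumed range. Only the direction is secure.

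**Conclusion.** The point holds as a worthwhile improvement, not a flaw that invalidates the plan. The main PDQ-39 analysis fixes the baseline coefficient at 1, the QALY base case fixes it at 0, and no main or base-case analysis estimates it.

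At middling correlations the gain is moderate: at r = 0.5, about 23% of variance for either outcome. For PDQ-39 it almost vanishes near r = 0.9. The downside outside the break-even limits is about 2% of variance. These sizes rest on assumed r, equal PDQ-39 SDs at the two time points and the protocol's planning SDs; the QALY SD of 0.35 is an upper value. The algebra itself is exact.

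**What to change.** 1. **Main clinical analysis:** linear regression of 12-month PDQ-39 on arm, baseline PDQ-39 and centre-experience stratum, with the t-test on change as supportive. Regressing change on the same terms gives the same arm estimate, so the SAP's change outcome can stay.
2. **Cost-utility base case:** within each of the 2,500 bootstrap samples, regress QALYs on arm and baseline utility. Carry the adjusted difference into the ICUR, net health benefit and acceptability curve. Keep the unadjusted comparison as supportive and the subtraction as a scenario.
3. **Cost-effectiveness analysis:** adjust the PDQ-39 effect for baseline PDQ-39 in the same way.
4. **Sample size text:** restate the 11.9-point figure with the SD or correlation that fits the chosen analysis.

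The cost is SAP and HEAP wording plus programming, since the regression must run through the multiple imputation and the bootstrap. No new data are needed. The stratum terms cost a little more: roughly 0.4–2.3% of variance in a simulation assuming four strata and blocked randomisation. The SAP says it was finalised before database lock; if analysis has since begun, report the adjusted results labelled as added.

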This design of the study was an RCT with ancillary patient preference observational arms which is also known as a "patient preference trial" or "comprehensive cohort study".³ In the RCT, patients with PD who met the inclusion criteria and who were willing to be randomized between CLI and DBS treatment were assessed for eligibility for both treatments. Eligible patients were randomized using online computer software (ALEA, Amsterdam UMC). Quality of life, costs, disability, PD specific motor and non-motor symptoms, neuropsychiatric comorbidities and caregiver burden were assessed 12, 24 and 36 months after initiation of advanced therapy (*i.e.*, CLI and DBS). Furthermore, at three, six, and nine months follow-up, additional assessments regarding costs, utilities and adverse events were planned.

It was expected that only a proportion of patients would be willing to be randomized between the two freely available therapies. Patients who were eligible to participate in the RCT but were not willing to be randomized, were asked to participate in the ancillary patient preference observational study. The observational study arms served primarily to determine the extent of the external validity of the RCT-results. Furthermore, data from RCT patients were pooled with data from the patients participating in the ancillary patient preference observational study, to compare specific clinical outcomes in a larger population. We aimed to randomize a total of 66 patients. There was no minimum of participants in the ancillary patient preference observational arms. Although an open-label study, data collection was performed by investigators who had no therapeutic relationship with study participants. Study data was not accessed by treating physicians. Treating physicians were aware of patients' study participation and allocated treatment if appropriate. Patients were treated in accordance with the center specific usual care regarding the procedures (*e.g.*, planning of DBS approach, usage of general anesthetics during placement of the DBS electrodes, possible pre-CLI medication test phase, and dose or device settings).

Synopsis of study protocol development

The first patient was included in December 2014. During the study, new insights and potential weaknesses in the original design were addressed in (substantial) amendments of the study protocol. Major adjustments are presented below. If applicable, this is also addressed in the relevant following paragraphs.

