In the initial design of the study, patient randomization was stratified according to both experience of the including center and the response to a supra-threshold levodopa-dose. A center was considered experienced in CLI or DBS treatment if in the previous two years at least five patients per year were started with CLI or DBS respectively in that center. Centers were able to change in stratum in case experience grew. Yet, four different strata based on experience of the including center (*i.e.*, little and much experience for both CLI and DBS) with two strata of levodopa response, would have led to a total of eight strata. This would lead to too few patients in at least some strata, considering the planned number of patients to be randomized. To reduce the number of strata, the protocol was amended in 2016 to include only stratification according to experience with both therapies.

In the original study protocol, a follow-up period of 12 months was described, but it was already stated that a longer follow-up period was desirable for a more reliable assessment and prediction of long-term effects and costs. After acquisition of additional funding, 24 and 36 months follow-up visits were added to the study protocol in 2017. All patients included were offered to participate in the extended follow-up. This statistical analysis plan describes the statistical analysis of the major outcomes of the first 12 months follow-up of the INVEST study, and not the ongoing 24- and 36-month follow-ups.

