For other clinical outcomes at 12 months, the last observation was carried forward if available from another visit (excluding baseline). For baseline characteristics, missing values were not imputed. For displaying baseline characteristics, the numerator and denominator were stated for dichotomous

variables (e.g., male: 5/15). For continuous variables, the number of patients for whom the variable was available was stated.

Study population

Baseline characteristics

For both the RCT mITT population and for the ancillary patient preference population, baseline characteristics were presented in Table SAP1. Categorical baseline characteristics were summarized by presenting counts and percentages. Visual inspection was used for assessment of normality of data distributions. Continuous, normally distributed variables were summarized by presenting the means and standard deviations. Continuous, non-normally distributed and ordinal variables were summarized by presenting the medians and interquartile ranges. Formal statistical tests were not performed to examine baseline differences between treatment groups. No bootstrapping was used for presentation of the baseline characteristics.

Table SAP1. Baseline characteristics

	CLI-RCT (n)	DBS-RCT (n)	CLI- observational (n)	DBS- observational (n)
Age (years)				
Sex, F (% n/N)				
Time since PD diagnosis (years)				
Hoehn and Yahr stage in on-drug state				
Levodopa-equivalent daily dose (mg/day)				
MDS-UPDRS part III score			NA	NA
- off-drug state				
- on-drug state				
- improvement off- to on-phase (%)*				
Parkinson's disease cognitive rating score			NA	NA
Level of experience of treating center with CLI and DBS treatment (%)**				
- Experienced in CLI, not in DBS				
- Experienced in DBS, not in CLI				
- Experienced in both CLI and DBS				
- Little experience in both CLI and DBS				

CLI: continuous intrajejunal levodopa infusion, DBS: deep brain stimulation, F: female, MDS-UPDRS: Movement Disorder Society's Unified Parkinson's Disease Rating Scale, mg: milligrams, NA: not available, RCT: randomized controlled trial

** Improvement: (score in off-drug state minus score in on-drug state) divided by score in off-drug state*

***Experienced in DBS/CLI: ≥ 5 patients treated per year in the two years previous to including the patient with the respective treatment in the treating center. A center may have changed in level of experience over time.*

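### The SAP's additional PDQ-39 regression omits levodopa response, which protocol 8.8 names as a covariate, and gives no reason; the effect is modest and the repair costs about one degree of freedom.

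*SAP*

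**What the plan says.** **Protocol, version 7 (October 2019).** Section 8.8 puts a two-group t-test first and a multiple linear regression second. The regression takes in baseline PDQ-39 and "the stratifying variables (experience of the including centre with DBS and CLI; response to Levodopa", plus relevant baseline imbalances if needed. Section 7.2, on randomisation, lists one stratification factor only: the including centre's experience with the two therapies.

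**SAP (March 2022).** Under Synopsis of study protocol development, the initial design is described: "patient randomization was stratified according to both experience of the including center and the response to a supra-threshold levodopa-dose". Eight strata were judged too many for the planned number of patients, and "the protocol was amended in 2016 to include only stratification according to experience with both therapies". The same synopsis dates the start: "The first patient was included in December 2014".

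Under Analysis of main clinical outcome, the main test is the between-group difference in change in "total PDQ-39 summary index score in the mITT population, using a two-group *t*-test". A multiple linear regression is additional, "taking into account the stratifying variable (level of experience of the treatment center". Any other covariate enters only through the clause "if necessary) clinically relevant baseline imbalances".

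Table SAP1 lists a baseline measure of levodopa response for the RCT arms, defined in its footnote as "Improvement: (score in off-drug state minus score in on-drug state) divided by score in off-drug state", applied to MDS-UPDRS part III. It is marked not available for the observational arms.

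**The concern.** The SAP cites protocol version 7 as its source, and its synopsis explains other departures: the change of strata, the dropped repeated-measures analysis and the move from ITT to mITT. It does not mention that a covariate named in protocol 8.8 has gone. The reason given for simplifying randomisation, thinly filled strata, does not carry over to a single regression term.

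Three things are at stake, none of them large.

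- For patients allocated under the two-factor scheme, an analysis that ignores a prognostic stratification factor overstates the standard error.
- For later patients the factor is not balanced by design. The mITT population also leaves out randomised patients who did not receive their allocated treatment, so balance achieved at randomisation is not assured in the set analysed.
- Levodopa response can now enter only if the analysts judge an imbalance relevant after seeing the data. The SAP gives no threshold or variable list, the trial is open label, and the study group's own investigators run the analysis.

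**Working it through.** **1. The passages side by side**

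| Place | Levodopa response |
|---|---|
| SAP synopsis, initial design | stratification factor, two levels |
| SAP synopsis, after the 2016 amendment | not a stratification factor |
| Protocol v7, 7.2 | not a stratification factor |
| Protocol v7, 8.8 | named as a stratifying variable and covariate |
| SAP, Analysis of main clinical outcome | not named |

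The strata argument: 4 experience strata × 2 levodopa strata = 8, and 66 / 8 = 8.25 patients per stratum on average. That is a sound reason to simplify randomisation. As a covariate, the factor costs one degree of freedom.

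**2. The plan's own PDQ-39 figure (protocol 4.4)**

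Inputs: 26 evaluable per group, SD 15, two-sided alpha 0.05, power 80%. The exact two-sample t calculation gives a detectable difference of 11.89, which reproduces the stated 11.9. Power for 11.9 points is 80.1%.

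**3. Adding one covariate**

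Let r be the correlation of levodopa response with the PDQ-39 outcome within arms. The documents give no value, so a range is assumed. The residual SD is 15 × √(1 − r²), and the degrees of freedom fall from 52 − 2 = 50 to 49. Power comes from the noncentral t distribution with 26 per group.

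| r (assumed) | SE ratio √(1 − r²) | SE reduction | Power for 11.9 | Detectable difference |
|---|---|---|---|---|
| 0 | 1.000 | 0% | 80.1% | 11.89 |
| 0.1 | 0.995 | 0.5% | 80.5% | 11.83 |
| 0.2 | 0.980 | 2% | 81.6% | 11.65 |
| 0.3 | 0.954 | 5% | 83.6% | 11.34 |
| 0.5 | 0.866 | 13% | 89.9% | 10.30 |

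The r = 0 row is the price if the covariate is useless: power moves from 80.10% to 80.07%. The table borrows the protocol's SD of 15 for PDQ-39 scores, whereas the SAP analyses change, so it shows relative size only.

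**4. Direction of the error when the factor is ignored**

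Let f be the share of analysed patients allocated under the two-factor scheme (not stated in the documents). If stratification balanced the factor fully in that share, the true variance of the group difference is about (1 − f r²) times the variance the analysis uses. The true two-sided type I error is then about 2 × [1 − Φ(1.96 / √(1 − f r²))].

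- f = 0.25, r = 0.1: 0.0497
- f = 0.5, r = 0.3: 0.0449
- f = 1, r = 0.5: 0.0236

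Every value is at or below the nominal 0.05. The last is an outer bound: f = 1 would need every analysed patient to predate the amendment, and two coarse strata balance only part of a continuous factor.

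**5. Availability**

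Protocol 7.3 plans MDS-UPDRS assessments in standardised OFF and ON phases at visit 1, before the eligibility discussion and randomisation. The ON phase follows a supra-threshold levodopa dose. The measure is therefore planned before randomisation for every RCT patient.

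**The case against.** The strongest reply is that protocol 8.8 is probably a leftover. Section 7.2 lists centre experience alone, the 2016 amendment removed levodopa response from randomisation, and the SAP adjusts for the one factor that remains. On that reading the SAP follows the current design and the defect lies in the protocol. This stands in part: the documents do not show that the SAP model is wrong. It does not explain why the SAP is silent, and it does not change how the earlier patients were allocated.

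Other points that stand:

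- The main clinical test ignores every stratification factor under both documents, and the primary outcomes are economic. The bootstrapped comparisons in the health economics plan do not use this regression.
- The clause on baseline imbalances is also in protocol 8.8, and Table SAP1 would display levodopa response by arm. The route into the model exists; it is just not fixed in advance.
- Protocol 7.3 treats too small a medication effect as a possible contraindication. That narrows the range of the covariate and tends to lower r, so 0.5 is the least plausible end.

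A reader might also infer more than the documents support:

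- *That type I error is inflated or the main result is invalid.* Step 4 shows the error is conservative, and the main t-test is the same with or without this covariate.
- *That the measure is complete in all randomised patients.* It is planned for all of them, but Table SAP1 covers the mITT population, completeness is not reported, and missing baseline values are not imputed.
- *That protocol 8.8 requires the continuous percentage improvement.* The factor used for randomisation had two strata, and neither their measure nor their cut-off is given.
- *That the trial regards levodopa response as a predictor of PDQ-39 change.* No section says so.

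**Conclusion.** The discrepancy is real and unexplained. Protocol 8.8 names two stratifying variables for the regression, the SAP keeps one, and protocol 7.2 disagrees with 8.8. It is worth correcting because pre-specification removes a choice made after seeing the data and respects the earlier allocation scheme at almost no cost.

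The size is modest. It touches an additional analysis, errs on the conservative side, and the possible gain in precision runs from about 0.5% to 13% of the standard error for assumed r of 0.1 to 0.5. Two unknowns limit any firmer statement: that correlation, and the number randomised before the amendment. That some patients were randomised under the two-factor scheme is itself inferred from the December 2014 first inclusion and the 2016 amendment.

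**What to change.** 1. In the SAP's additional multiple linear regression, pre-specify baseline levodopa response for all RCT patients in the analysis, whatever the observed imbalance, alongside centre experience. A practical form is the continuous percentage OFF-to-ON improvement in MDS-UPDRS III already defined in Table SAP1. This coding is a proposal and should be labelled as one, since the factor used for randomisation had two strata.
2. Add a rule for missing baseline values of this covariate, for example replacing them with the mean over both arms, so that no patient is lost. The SAP's statement that baseline values are not imputed needs a matching exception.
3. Reconcile protocol 7.2 and 8.8 with the SAP's synopsis and its Analysis of main clinical outcome. If the team prefers to leave the covariate out, the SAP should say so and give the reason.

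The pooled regression with the preference cohort cannot take this covariate, because the measure is not available there; the change concerns the RCT regression only.

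Cost: about one degree of freedom, a few lines of text and syntax, and no new visits or measurements.
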